# ROLLOVER TO THE OPEN-LABEL EXTENSION TRIAL (ARGX-113-1803)

Patients who complete the 24-week trial period have the possibility to enter the open-label extension trial (ARGX-113-1803) to receive efgartigimed 10 mg/kg IV. The platelet counts from the ARGX-113-1801 trial will be taken into account to assess the dosing frequency in ARGX-113-1803.

### CONCURRENT ITP THERAPY

Patients receiving at least 1 permitted concurrent ITP therapy are eligible for the trial, if the dose and schedule have remained unchanged in the last 4 weeks before randomization (ie, visit 1). Permitted concurrent ITP medications include oral corticosteroids, oral immunosuppressants, dapsone/danazol, fostamatinib and/or oral TPO-RAs (inclusion criterion n°6, Section 4.3.1). Dose and frequency of permitted concurrent ITP therapies should remain unchanged during the trial.

As of week 12, the start or an increase in the dose and/or schedule of permitted concurrent ITP therapy is allowed for patients who have an "insufficient response" (ie, no platelet count of  $\geq 30 \times 10^9$ /L in any of the visits during the last 4 weeks). These patients will be considered as "non-responders" for the primary endpoint analysis. At the discretion of the investigator, the dose and/or schedule of the concurrent ITP therapy can be returned to the baseline levels.

Exceptions are patients who are receiving concurrent treatment with oral TPO-RAs in whom dose changes are permitted at label-defined platelet thresholds, and patients who are receiving concurrent treatment with fostamatinib, in whom dose changes or stopping of treatment is allowed in label-defined conditions.

argenx BVBA Confidential Page 45 of 162

All changes or discontinuations in concurrent ITP therapy (type, dose, frequency, date of discontinuation and resumption) should be appropriately indicated in the electronic case report form (eCRF). The patient does not need to be discontinued from the trial.

Patients not receiving concurrent ITP therapy are also eligible for the trial.

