### 3. TRIAL ENDPOINTS

# 3.1. Primary Endpoint

• Proportion of patients with chronic ITP with a sustained platelet count response defined as achieving platelet counts of at least 50×10^9/L for at least 4 of the 6 visits between week 19 and 24 of the trial.

Patients who discontinue treatment prior to visit 24 due to lack of efficacy (eg, more than 3 occurrences of rescue therapy) or due to an AE, and who have not achieved sustained platelet count response between week 19 and 24, are considered non-responders. Patients who receive rescue therapy at week 12 or later, or for whom dose and/or frequency of concurrent ITP therapies have increased at week 12 or later, are also considered non-responders.

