### **6.8.1.** Concurrent ITP Therapy

Patients receiving at least 1 permitted concurrent ITP therapy are eligible for the trial, if the dose and schedule have remained unchanged in the last 4 weeks before randomization (ie, visit 1).

Permitted concurrent ITP medications include oral corticosteroids, oral immunosuppressants, dapsone/danazol, fostamatinib and/or oral TPO-RAs.

argenx BVBA Confidential Page **61** of **162** 

Patients not receiving concurrent ITP therapy are also eligible for the trial if they have not received prior ITP therapy for at least 4 weeks prior to baseline (inclusion criterion 6).

Dose and frequency of permitted concurrent ITP therapies should remain unchanged during the trial.

Exceptions are patients who are receiving concurrent treatment with TPO-RAs in whom dose changes are permitted at label-defined platelets thresholds, and patients who are receiving concurrent treatment with fostamatinib, in whom dose changes or stopping of treatment is allowed in label-defined conditions.

As of week 12, the start or an increase in the dose and/or schedule of permitted concurrent ITP therapy is allowed for patients who have an "insufficient response" (ie, no platelet count of  $\geq 30 \times 10^9$ /L in any of the visits during the last 4 weeks). These patients will be considered as "non-responders" for the primary endpoint analysis. At the discretion of the investigator, the dose and/or schedule of the concurrent ITP therapy can be returned to the baseline levels.

Any change in concurrent ITP therapy should appropriately be recorded in the eCRF.

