3.5 PRIOR AND CONCOMITANT THERAPIES

3.5.1 Available data

All therapies are coded using the September 2021 version of the WHO-DRUG Dictionary. Anatomical therapeutic chemical (ATC) selection is performed. The ATC coding up to level 4 is available in the clinical database. For each therapy, a start date or prior flag and stop date or ongoing flag are collected.

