3.5.2 Derivation rules

Based on their start and stop date, therapies will be allocated into 1 or both of the following categories:

- Prior: any therapy that strictly started before the first IMP dose date.
- Concomitant: any therapy that was taken on or after the first IMP dose date.

A medication that started before the first IMP dose date and continued during the study will be classified as both prior and concomitant.

SGS	Statistical Analysis Plan	
ARGX-113-1801	Final analysis	Final 1.0 of 28MAR2022

The ITP-specific therapies will be allocated to the following categories:

- Prior ITP therapy: stopped prior to first IMP dose date
- Continued concurrent ITP therapy: started prior to first IMP dose date and continued after first IMP dose date
- New concurrent ITP therapy: started after first IMP dose date

Therapies with (partially) missing dates will be allocated to each category unless the available parts of the therapy start or stop date or the started prior to trial/ongoing at end of trial flag provide evidence not to do so.

Type of ITP therapy:

- Corticosteroids: selection based on ATC2 = 'H02'
- IVIG, anti-D: selection based on ATC2 = 'J06' or CMDECOD = 'ANTI-D IMMUNOGLOBULIN'
- Thrombopoietin-receptor agonists (TPO-RA): selection based on CMDECOD = ('AVATROMBOPAG MALEATE' or 'AVATROMBOPAG' or 'ELTROMBOPAG' or 'ELTROMBOPAG OLAMINE' or 'ROMIPLOSTIM')
- Fostamatinib: selection based on CMDECOD = ('FOSTAMATINIB' or 'FOSTAMATINIB DISODIUM')
- Other immunosuppressants (azathioprine, cyclophosphamide, cyclosporine A, mophetil mycophenolate, vinca alkaloids): selection based on CMDECOD = ('AZATHIOPRINE' or 'CICLOSPORINE' or 'CYCLOPHOSPHAMIDE' or 'MYCOPHENOLATE MOFETIL' or 'MYCOPHENOLATE SODIUM' or 'SIROLIMUS' or 'VINBLASTINE SULFATE' or 'VINCRISTINE' or 'VINCRISTINE SULFATE')
- Danazol: selection based on ATC4 = 'G03XA'
- Dapsone: selection based on ATC4 = 'J04BA'
- Anti-CD20 (Rituximab): selection based on ATC4 = 'L01XC'
- Other: ITP therapies that are not in any of the previous 9 categories

Rescue ITP therapy will be allocated to the following categories:

- methylprednisolone, dexamethasone, prednisone: selection based on ATC4
 = "H02AB"
- immunoglobulins given IV (IVIg): selection based on ATC4 = "J06BA"
- IV anti-D: selection based on CMDECOD = 'ANTI-D IMMUNOGLOBULIN'
- platelet transfusions: selection based on CMDECOD = 'PLATELETS, CONCENTRATED'
- other: rescue medications that are not in any of the 4 previous categories

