4.1.2.1 PRIMARY ENDPOINT

The primary endpoint is the proportion of patients with a sustained platelet count response (week 19 - 24) within the adult population with chronic ITP.

A patient is considered a responder, i.e. has a sustained platelet count response, if he/she shows platelet counts of at least 50×10^9 /L for at least 4 of the 6 analysis visits between weeks 19 and 24 of the study. ($\geq 50 \times 10^9$ /L prim resp).

The main analysis on the primary endpoint will use the 'composite variable strategy' in case of main intercurrent events using the Cochran-Mantel-Haenszel test (see also section 4.1.3.2). This strategy implies that when a main intercurrent event occurs, a patient is considered a non-responder, if the patient has not achieved sustained platelet count response before the occurrence of the main intercurrent event. This happens in the following situations:

- early discontinuation of treatment (prior to week 24) due to lack of efficacy (DSDECOD = "Lack of efficacy") or due to an AE
- initiation of rescue therapy at week 12 or later: relative day of start date of rescue medication ≥ target ADY of analysis visit corresponding to Week 12

SGS	Statistical Analysis Plan	
ARGX-113-1801	Final analysis	Final 1.0 of 28MAR2022

- increase of dose and/or frequency of concurrent ITP therapies or start of a new concurrent ITP therapy at week 12 or later:
 - (if start date concurrent ITP therapy ≥ target ADY of analysis visit corresponding to Week 12) and (dose > previous dose of the specific ITP therapy OR frequency > previous frequency of the specific ITP therapy)

AND

(if start date concurrent ITP therapy ≥ target ADY of analysis visit corresponding to Week 12) and (dose > dose of the specific ITP therapy at baseline OR frequency > frequency of the specific ITP therapy at baseline)

OR

• new ITP therapy

Note: if for frequency a change is detected, but it is not clear whether a real increase has taken place, it will be considered worse-case and analysed as increase (e.g.: Baseline value 'QD' changed to e.g. 'at will', 'as needed'; Baseline value 'As needed' changed to e.g. 'QD, ', 'continuous').

Missing values for reasons other than the main intercurrent events, will be imputed as described in section 4.1.2.5 (approach 1).

A complementary analysis for this primary analysis will use the 'treatment policy strategy' where these main intercurrent events are handled differently.

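### The SAP defines a 'new' ITP therapy by start date alone, so a baseline drug resumed at or below its baseline dose can trigger non-response

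*Protocol*

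**What the plan says.** **Protocol.** Sections 4.1 and 6.8.1 start from a rule of no change: "Dose and frequency of permitted concurrent ITP therapies should remain unchanged during the trial". The exceptions are oral TPO-RAs, whose dose may change at label-defined platelet thresholds, and patients on fostamatinib, "in whom dose changes or stopping of treatment is allowed in label-defined conditions". Section 4.1 adds that "All changes or discontinuations in concurrent ITP therapy (type, dose, frequency, date of discontinuation and resumption) should be appropriately indicated" in the eCRF. For the primary endpoint, Section 3.1 says that patients "for whom dose and/or frequency of concurrent ITP therapies have increased at week 12 or later, are also considered non-responders"; Section 8.4.1 lists the same trigger. Sections 4.1 and 6.8.1 also treat as non-responders those insufficient responders in whom a permitted ITP therapy is started or increased from week 12.

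**SAP.** Section 3.5.1 describes the data: "For each therapy, a start date or prior flag and stop date or ongoing flag are collected". Section 3.5.2 sorts ITP therapies by date: "Continued concurrent ITP therapy: started prior to first IMP dose date and continued after first IMP dose date" and "New concurrent ITP therapy: started after first IMP dose date". Neither category mentions a drug that is stopped and resumed. Section 4.1.2.1 has two routes to the intercurrent event. One is an increase, which must exceed both the previous and the baseline dose or frequency. The other, joined by OR, is the "start of a new concurrent ITP therapy at week 12 or later", with no such comparison. Section 4.1.2.2 uses both routes for extent of disease control without the week-12 limit. Item 7 of Section 4.1.2.3 compares with the previous level only, and has the same OR branch.

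**The concern.** The two routes treat the same patient differently. The increase route spares anyone whose background therapy is at or below its baseline level. The other route asks only whether the therapy is new, and the SAP's one written definition of that category is a start date after the first dose. If a resumed drug is entered with its own start date, it meets that definition even though it was taken at baseline and has not gone above its baseline dose.

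Several alpha-controlled results depend on this. The primary endpoint and both overall-population responder endpoints (key secondary endpoints 2 and 4) use the rule in 4.1.2.1. The first key secondary endpoint uses the wider version in 4.1.2.2. SAP 1.8 requires independent programming of the primary endpoint and extent of disease control. Two programmers could resolve the wording in opposite ways, or both could apply the written definition.

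**Working it through.** No figure in the plan depends on this rule, so there is none to reproduce. The check applies the rule to test cases.

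**1. Days at risk (SAP 2.2.4, Table 3).** The target day for week 4 + x is 29 + 7x.
- Week 12: 29 + 7×8 = 85.
- Week 22: 29 + 7×18 = 155. This is the earliest visit at which 4 of the 6 counts from week 19 can be complete.

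SAP 4.1.2.1 makes the patient a non-responder only if sustained response was not achieved before the event. A resumption is therefore harmless to the primary endpoint before day 85 or after the fourth qualifying visit. The exposed interval is at least 155 − 85 = 70 days.

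**2. The rule.** For a therapy starting on day 85 or later:
- Increase = (dose or frequency > previous) AND (dose or frequency > baseline).
- Event = Increase OR new.

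Reading A takes new from SAP 3.5.2 (start date after first dose). Reading B takes it as a drug not taken at baseline. Start day is 100 and doses are in arbitrary units. It is an inference that a resumption or dose step has its own start date: SAP 3.5.1 has start and stop dates per therapy, and 4.1.2.1 tests a start date together with a previous dose.

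| Case | Dose / previous / baseline | Increase | Event, A | Event, B | Item 7: dose > previous |
|---|---|---|---|---|---|
| Resumed at baseline dose, previous set to 0 | 50/0/50 | no | **yes** | no | yes |
| Resumed below baseline, previous set to 0 | 25/0/50 | no | **yes** | no | yes |
| Resumed at baseline, previous = last dose taken | 50/50/50 | no | **yes** | no | no |
| Tapered, then back to baseline | 50/25/50 | no | **yes** | no | yes |
| Reduced below baseline | 25/50/50 | no | **yes** | no | no |
| Raised above baseline | 75/50/50 | yes | yes | yes | yes |
| Drug absent at baseline | 50/0/0 | yes | yes | yes | yes |

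The readings differ in all five cases where therapy stays at or below baseline. Under A the increase route never decides a case. Item 7 counts a return to baseline after a taper as an increase even under B. Its result for a resumption depends on an undefined previous dose.

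**3. Extent of disease control.** SAP 4.1.2.2 handles every count strictly after the event as below 50×10⁹/L. Under A, a resumption at week 6 (day 29 + 7×2 = 43) would discount weeks 7 to 24, up to 24 − 6 = 18 counts.

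**4. Illustration of power.** The planning response rates are blacked out, so these are assumptions: 39 placebo and 78 efgartigimod patients (117 at 2:1), an unstratified two-sided 5% test, and an efgartigimod rate set to give 90% power.

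Power = Φ[(d − 1.96·SE₀)/SE₁], with SE₀ from the pooled rate and SE₁ from the separate rates.

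Example with placebo 5% and efgartigimod 28.5%: d = 0.235; pooled rate = (39×0.05 + 78×0.285)/117 = 0.2067; SE₀ = 0.0794; SE₁ = 0.0619; (0.235 − 0.1556)/0.0619 = 1.28; power 90.0%. Each lost responder lowers the efgartigimod rate by 1/78.

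| Assumed placebo | Efgartigimod | 0 lost | 1 lost | 2 lost | 3 lost |
|---|---|---|---|---|---|
| 2% | 22.8% | 90.1% | 86.9% | 83.0% | 78.4% |
| 5% | 28.5% | 90.0% | 87.0% | 83.3% | 79.1% |
| 10% | 36.6% | 90.2% | 87.4% | 84.0% | 80.2% |
| 15% | 43.5% | 90.1% | 87.3% | 84.1% | 80.4% |

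Exact enumeration for placebo rates of 3–10% gives much the same: about 87%, 82–84% and 77–80%.

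**The case against.** The strongest reply is that reading A defeats itself. If every entry dated after the first dose is new, the comparison with previous and baseline levels never matters and even a dose reduction is an event. The evident intent is reading B. SAP 4.1.2.1 also does not cite 3.5.2 for the term, whereas 3.3.2 and 4.1.4 cite that section when they rely on it. This stands: a reader might infer that the SAP has settled on counting any later record as new, and the documents do not support that. They contain a written definition that conflicts with an evident intent, and no text that resolves it.

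Other replies also stand in part:
- A reader might infer that the protocol expects interruptions. It does not. The general rule is no change, and stopping is expressly allowed only for fostamatinib. Resumption is recorded, so it is foreseen as data.
- A reader might say the protocol counts only increases. It also counts a start in insufficient responders, so the SAP's start branch has some basis. That basis does not reach a baseline drug resumed at or below its baseline dose in any other patient.
- A reader might infer that the loss falls mainly on efgartigimod responders. The documents link platelet thresholds to TPO-RA dose changes, not to stopping, and do not state the label conditions for fostamatinib. The direction is plausible but unproven.
- The treatment-policy analyses of the primary and first key secondary endpoints ignore these events, and intercurrent events are tabulated and listed. That would expose a problem, but would not change the alpha-controlled results.

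**Conclusion.** The concern holds as a conflict between the SAP's written definition and its own baseline comparison. Followed as written, the definition makes a patient who resumes a baseline drug at or below its baseline dose at week 12 or later a primary non-responder, unless sustained response was already achieved. In extent of disease control it discounts all later weeks, whenever the resumption occurs. It goes beyond the protocol's trigger, and SAP 6.1 does not list it as a change. Item 7 has a further fault: without a baseline comparison, a return to the baseline level counts as an increase.

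The size is unknown. The documents give no count of patients on a TPO-RA or fostamatinib, nor of interruptions. The power figures assume the response rates, an unstratified test in place of the planned Cochran-Mantel-Haenszel test, and losses in the efgartigimod arm only. They show sensitivity to a few patients and are not a forecast. The point should be settled because the two readings give opposite primary outcomes for the same patient and the correction is small.

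**What to change.** Before unblinding, amend SAP 3.5.2, 4.1.2.1, 4.1.2.2 and item 7 of 4.1.2.3 as follows.

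1. Define a new ITP therapy as an active substance not being taken at the first IMP dose. Pool salt forms and synonymous coded terms. SAP 3.5.2 itself lists two terms each for eltrombopag, avatrombopag and fostamatinib, so a definition by coded term could still label a resumed drug as new.
2. Send any resumption or later record of a baseline substance only through the above-previous AND above-baseline test of dose or frequency.
3. State how the previous dose is set after an interruption (zero, or the last dose taken).
4. Add the baseline comparison to item 7.

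The cost is one definition, its program and a short SAP amendment. The fields needed are already collected. This concerns only how records are derived for analysis and takes no view on how concurrent therapy should be managed.

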### **RESCUE THERAPY**

"Rescue therapy" is defined as an occurrence where the patient needs treatment with 1 or more rescue treatments. An "occurrence" is defined as a period of maximum 5 days where 1 or more rescue treatments are administered simultaneously or consecutively to the trial patient. The start date/time of the occurrence is the start of the administration of the first rescue treatment.

Rescue therapy is allowed post-baseline during the 24-week trial period for patients with a platelet count of  $<30\times10^9$ /L and 1 of the following:

- an immediate risk of bleeding or a clinically significant bleeding or wet purpura
- requirement for urgent or emergent surgery (elective surgeries must be postponed until trial completion)

The following rescue therapies are permitted:

- IV methylprednisolone up to 1 g/day×1-3 days, or oral dexamethasone up to 40 mg/day×1-3 days, or oral prednisone up to 1 mg/kg/day×1-2 days
- IVIg: up to 1 g/kg/day×1-2 days
- IV anti-D: up to 50-75 mcg/kg/day×1-2 days Note: Anti-D rescue therapy should not be given to Rh(D)-positive patients
- platelet transfusions

It is encouraged to inform the sponsor's designated contract research organization (CRO) medical monitor prior to initiating any rescue therapy.

In the event of rescue with IVIg or IV anti-D:

• If given at a visit where the investigational medicinal product (IMP) was due to be administered, the IMP should be withheld and administered at the next visit.

For rescue therapy with methylprednisolone, dexamethasone, prednisone, or platelet transfusions:

• Administration of the IMP continues during rescue therapy.

Patients who were receiving q2w dosing at the time of rescue therapy will have the IMP administration frequency increased to weekly.

argenx BVBA Confidential Page 46 of 162

For patients who receive rescue therapy, the platelet counts for 4 weeks after the first day of rescue treatment will not be used (ie, are censored) to assess whether or not the patient can transition to q2w treatment.

Patients requiring more than 3 occurrences of rescue therapy will discontinue from IMP.

### EARLY DISCONTINUATION FROM THE TRIAL

Any patient prematurely discontinuing the trial should perform the assessments listed for the Early Discontinuation visit as mentioned in the SoA (Table 1).

### TRIAL END

End-of-Trial is defined as last patient last visit in the ARGX-113-1801 trial.

# 4.2. Discussion of Trial Design

In the current trial, efgartigimod or placebo will be administered in patients with primary ITP, with the aim to evaluate the efficacy, safety, and impact on QoL of efgartigimod versus placebo.

This trial is designed as a randomized, double-blinded trial to evaluate the effect of efgartigimod and placebo administered as an IV infusion. The trial consists of a treatment period where all patients will initially receive weekly IV infusions from visits 1 to 4. From visits 5 to 16, the dosing frequency can be altered (ie, increased or decreased) according to specified rules.

The primary endpoint in this trial is the proportion of patients with chronic ITP that have a sustained platelet count response defined as achieving platelet counts of at least  $50 \times 10^9$ /L for at least 4 of the 6 visits between week 19 and 24 of the trial. Patients who discontinue treatment prior to visit 24 due to lack of efficacy (eg, more than 3 occurrences of rescue therapy) or due to an AE, and who have not achieved sustained platelet count response between week 19 and 24, are considered non-responders. Patients who receive rescue therapy at week 12 or later, or for whom dose and/or frequency of concurrent ITP therapies have increased at week 12 or later, are also considered non-responders.

The key secondary endpoints assess the efficacy of efgartigimod focusing on measures of response derived from platelet counts, and the incidence and severity of bleeding.

The choice of a 10-mg/kg IV dose of efgartigimod was made because it has been shown to be well tolerated, to consistently achieve close to maximal PD effect, and to be associated with a clinical meaningful effect on platelet counts (see Section 1.3). Based on the transient clinical responses observed following short term 4-week treatment in the phase 2 trial, a personalized chronic dosing regimen guided by treatment response is proposed in line with the chronic nature of the disease: a continuous weekly or q2w dosing regimen of 10 mg/kg.

Platelet count is an objective measure and is the accepted marker of treatment effect in ITP.

argenx BVBA Confidential Page 47 of 162

